6.5. STATISTICAL TESTS

No statistical inferential procedures will be performed for this study.

6.6. COMMON CALCULATIONS

For quantitative measurements, change from baseline will be calculated as:

- Test Value at Visit X – Baseline Value

6.7. SOFTWARE VERSION

All safety and efficacy analyses will be conducted using SAS® Version 9.2 or higher (SAS Institute, Inc., Cary, North Carolina).

7. STATISTICAL CONSIDERATIONS

7.1. MULTICENTER STUDIES

This study will be conducted by multiple investigators at multiple centers within the United States. Center pooling will not be carried out for use in analyses for this study.

7.2. MISSING DATA

For safety and efficacy analyses, observed values will be used and no imputation will be made for missing data.

Missing dates for Adverse Events (AEs) and concomitant medications will be imputed using the rule provided in [Appendix 1](#). If the intensity is missing for any AE, its intensity will be classified as Severe in the summary tables. If the assessment of relationship of the AE to study treatment is missing, it will be classified as Related in the frequency table of possible related treatment emergent AEs.

7.3. MULTIPLE COMPARISONS/ MULTIPLICITY

No adjustment for multiplicity will be performed since the analyses of safety and efficacy endpoints are descriptive.

7.4. EXAMINATION OF SUBGROUPS

No subgroup analyses will be performed for this study.

Document: C:\Users\q832483\Documents\Insy CSR\Pending\Ready for QC\New folder\Statistical Analysis Plan.docx
Author: [REDACTED] Version Number: V1.0 Final
Version Date: 04APR2017

Template No: CS_TP_BS016 – Revision 3
Effective Date: 01May2012

Reference: CS_WI_BS005

However analyses will be displayed by age category as follows:

- Infants = 1 to <2 years of age
- Children = 2 to <12 years of age
- Adolescents = 12 to ≤17 years of age

Age categories are based on the subject's age at the beginning of their previous study.

In addition, some relevant results observed during the follow-up period (between the Final visit and the Follow-up visit) or assessed at the Follow-up visit will be presented by CBD status (i.e. subjects who continue to receive CBD after their Final visit versus those who stop receiving CBD after their Final visit). Such analyses are further described in the following sections.

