3.4.3 Subject Withdrawal

All subjects are free to withdraw from participation in the study at any time, for any reason, specified or unspecified, and without prejudice to further treatment.

The criteria for enrollment are to be followed explicitly. If a subject who does not meet enrollment criteria is inadvertently enrolled, that subject should be withdrawn from the study and the Sponsor must be contacted. An exception may be granted in rare circumstances where there is a compelling safety reason to allow the subject to continue. In these rare cases, the Investigator must obtain documented approval from the Sponsor to allow the subject to continue in the study.

In addition, subjects will be withdrawn from the study in the following circumstances (i.e., stopping criteria):

- The Investigator decides that the subject should be withdrawn for safety
 - If the decision to remove the subject from the study is made because of an intolerable AE or a clinically significant laboratory value associated with the use of the investigational product, the investigational product is to be discontinued, appropriate measures taken, and the Sponsor notified immediately.
- Subject is unwilling to continue in the study and/or the subject or caregiver withdraw consent
- Lack of compliance with protocol
- Investigator or Sponsor stops the study for any reason
- Subject becomes pregnant
- Laboratory values demonstrate a subject serum ALT or AST level >3 times ULN (requires confirmation within 2 days)
- Laboratory values demonstrate a subject serum total bilirubin in excess of >2 times the ULN (requires confirmation within 2 days)
- Subject is enrolled in error
- Subject is lost to follow-up.
 - Lost to follow-up will be defined as a subject failing to attend planned study visits or to response to contacts by the study center staff contacts after

documented 2 attempts and for whom no other contact information is available.

Subjects who discontinue the study early will be asked to complete the Final Visit/Discontinuation Visit, with assessments to be completed as indicated in Table 1.

Subjects may elect to withdraw from study treatment with the possibility of completing remaining visits to allow for monitoring until end of study. All data taken through the subject withdrawing consent or the Investigator or Sponsor decision to discontinue the study, as well as data from the Final Visit/ Discontinuation Visit, will be collected for discontinued subjects.

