5.3 Final Visit/Discontinuation Visit (Visit 10) ±10 days

Each subject will complete a Final Visit/Discontinuation Visit regardless of when they complete/stop the study. Should a subject's participation be terminated according to study stopping criteria (see Section 3.4.3), this will be considered a Discontinuation Visit. For both, the following procedures will be completed:

- Record recent medication history including current AEDs, vitamins, herbal preparations, blood products, and over-the-counter drugs
- Record concomitant medications and concomitant procedures
- Obtain a 12-lead ECG
- Record vital signs (blood pressure, heart rate, respiratory rate, and temperature measurements)
- Draw blood samples for hematology and chemistry (fasting NOT required) and record whether subject was fasting at time of collection in the eCRF
- Obtain a urine sample for urinalysis
- Obtain a urine sample for serum β -hCG pregnancy test in female subjects of childbearing potential
- Perform physical examination (see Section 6.1.5.2), including height and weight
- Perform a brief neurology examination (see Section 6.1.5.2)
- Review and collect subject seizure and dosing diary and collection of completed pages, if applicable
 - Diary data will be collected for one week (7 days) prior to Visit 10.
- Collect investigational product
- Record AEs and SAEs

- Complete blood draw for plasma levels
- Administer Investigator CGI-I and CGI-S
- Administer parent(s)/caregiver(s) CGI-I and CGI-S
 - When appropriate, subjects will complete the CGI-I and CGI-S for themselves.
- Administer IPES
 - The IPES is validated for subjects who are 2 to 16 years of (developmental) age. Due to developmental delay characteristic of the study population, subjects through 18 years of chronological age will complete the IPES.
- Administer VABS
 - The VABS is validated for use in subjects from birth to 90 years of age.
- Administer C-SSRS (if appropriate).

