17.1. ADVERSE EVENTS

Adverse Events (AEs) will be coded using the latest version of MedDRA central coding dictionary.

Treatment emergent adverse events (TEAEs) are defined as AEs that first occur or worsen in severity after the first administration of the study medication.

See [Appendix 1](#) for handling of partial dates for AEs. In the case where it is not possible to define an AE as treatment emergent or not, the AE will be classified by the worst case; i.e. treatment emergent.

An overall summary of number of subjects within each of the categories described in the sub-section below, will be provided as specified in the templates. In the summaries, AEs will be counted only once per subject. Only those AEs that begin between start and end of study will be summarized.

Each summary described in Adverse Event section (except [Section 17.1.2](#) and [Section 17.1.3](#)) will be repeated for TEAEs observed during the Follow-up period and presented by CBD status.

Listings will include TEAEs and Non-TEAEs.

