17.3.1. LABORATORY REFERENCE RANGES AND MARKEDLY ABNORMAL CRITERIA

Quantitative laboratory measurements will be compared with the relevant laboratory reference ranges in SI units and categorized as:

- Low: Below the lower limit of the laboratory reference range (LLN).
- Normal: Within the laboratory reference range (upper and lower limit included).
- High: Above the upper limit of the laboratory reference range (ULN).

Document: C:\Users\q832483\Documents\Insy CSR\Pending\Ready for QC\New folder\Statistical Analysis Plan.docx
Author: [REDACTED] Version Number: V1.0 Final
Version Date: 04APR2017

Template No: CS_TP_BS016 – Revision 3
Effective Date: 01May2012

Reference: CS_WI_BS005

STATISTICAL ANALYSIS PLAN: PROTOCOL INS011-14-030

Page 29 of 40

In addition to the high and low quantitative laboratory assignments (as identified by means of the laboratory reference ranges), markedly abnormal values for liver function tests (LFTs) will also be identified and summarized by time point and age category for:

- Alanine aminotransferase (ALT) level >3 times ULN
- Aspartate aminotransferase (AST) level >3 times ULN
- Total bilirubin in excess of >2 times ULN

Markedly abnormal values for LFTs observed at the Follow-up visit will also be summarized by CBD status.

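### The two-level CBD status used for follow-up results does not separate early discontinuers from completers who stopped, and does not say where subjects belong whose last dose came before Visit 10

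*SAP*

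**What the plan says.** SAP 7.4 plans no subgroup analyses. It adds that some results from the follow-up period, or assessed at the Follow-up visit, will be shown by CBD status: "subjects who continue to receive CBD after their Final visit versus those who stop receiving CBD after their Final visit". It defines the follow-up period as the time between those two visits.

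The split is then used widely: procedures and medications including AEDs (SAP 12 and 13), CGI and IPES (16.2.2.3), deaths (17.2), laboratory results (17.3), vital signs and weight (17.5) and C-SSRS (17.7.3). For adverse events, SAP 17.1 says most summaries "will be repeated for TEAEs observed during the Follow-up period and presented by CBD status". For liver tests, SAP 17.3.1 says: "Markedly abnormal values for LFTs observed at the Follow-up visit will also be summarized by CBD status". The flags there are "Alanine aminotransferase (ALT) level >3 times ULN", the same multiple for AST, and total bilirubin above 2 times ULN.

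On who reaches these visits, Protocol 5.3 says: "Each subject will complete a Final Visit/Discontinuation Visit regardless of when they complete/stop the study". Protocol 5.4 then schedules a Follow-up Visit for all subjects two weeks later. Among the withdrawal criteria in Protocol 3.4.3 are "Laboratory values demonstrate a subject serum ALT or AST level >3 times ULN (requires confirmation within 2 days" and "Laboratory values demonstrate a subject serum total bilirubin in excess of >2 times the ULN (requires confirmation within 2 days". When a subject is removed for an adverse event or laboratory finding attributed to the product, "the investigational product is to be discontinued, appropriate measures taken, and the Sponsor notified immediately". Protocol 4.1.2 and SAP 3.1 ask that any taper, for subjects not entering Expanded Access, be finished before Visit 10.

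**The concern.** Whether a subject is still taking CBD at Visit 11 depends on what happened during treatment and on the family's and investigator's choice. A single stopped column could mix two different kinds of subject: those who finished the planned treatment and then came off, and those who left early, some because of toxicity. The continued column would consist largely of subjects who tolerated the drug to the end.

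The liver table is the sharpest case. A subject can be withdrawn for exceeding a cut-off and then be checked about two weeks later against the same cut-off. A higher proportion in the stopped column could then be read as an effect of withdrawal, or as reassurance about continuing, when it reflects who was placed in that column.

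There is a second gap. Laboratory results at follow-up are compared only with Baseline 1 and Baseline 2 (SAP 6.2 and 17.3). Both precede the first dose in this study, so no planned group summary shows change from the last value on treatment.

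**Working it through.** The plan gives no figure for the CBD-status split, so there is nothing to reproduce. The check is of the definition, followed by a purely hypothetical illustration.

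**Step 1: where each kind of subject falls under SAP 7.4.**

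- Completes 48 weeks and enters Expanded Access: continued.
- Completes and stops at the Final visit without a prior taper: stopped.
- Completes with a planned taper: last dose is before Visit 10 (Protocol 4.1.2), so the subject does not literally stop after the Final visit. Not assigned.
- Withdrawn early, with last dose before the Discontinuation Visit: has Visit 10 and is scheduled for Visit 11. Not assigned literally; stopped on the natural two-group reading.
- Leaves treatment but keeps attending visits (allowed by Protocol 3.4.3): may be off drug for a long time by Visit 11. Not assigned literally.

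On the literal reading, the last three kinds drop out of the tables. On the natural reading, they are pooled with elective stoppers.

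**Step 2: selection rule against tabulated outcome.**

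- ALT or AST: withdrawal above 3 times ULN (Protocol 3.4.3); flag above 3 times ULN (SAP 17.3.1).
- Total bilirubin: withdrawal above 2 times ULN; flag above 2 times ULN.

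The cut-offs are identical. The only difference is that withdrawal needs confirmation and the SAP flag does not mention it. On the natural reading, the liver table is therefore partly selected on its own outcome. No other table has a documented overlap of this kind.

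**Step 3: hypothetical illustration.** Every input is assumed. Let t be subjects withdrawn for liver values, e elective stoppers, q the share of t still above a cut-off at Visit 11, and b a background rate common to elective stoppers and continuers. Stopping has no effect.

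Stopped rate = (t·q + e·b)/(t + e); continued rate = b; difference = t(q − b)/(t + e).

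With b = 2%:

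- t = 4, e = 20, q = 50%: (2 + 0.4)/24 = 10.0% against 2.0%, difference +8.0 points.
- t = 1, e = 40, q = 25%: (0.25 + 0.8)/41 = 2.6%, difference +0.6 points.
- t = 8, e = 10, q = 75%: (6 + 0.2)/18 = 34.4%, difference +32.4 points.
- t = 8, e = 10, q = 0: 0.2/18 = 1.1%, difference −0.9 points.

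Over t = 1 to 8, e = 10 to 40 and q = 0 to 75%, the last two are the extremes. The sign depends on whether q exceeds b, which the documents do not tell us. If early withdrawals have their own column, the difference is zero in every scenario, because elective stoppers and continuers were assumed to share b.

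**The case against.** A reader might infer that every subject withdrawn for toxicity enters the stopped column, and that the liver, adverse-event and global-status contrasts are all biased in a known direction. The documents do not support that.

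- **Allocation is not stated.** The SAP never places early discontinuers. Expanded Access entry rules are not given. Early discontinuers are only asked to attend the Final visit (Protocol 3.4.3), and those lost to follow-up contribute no Visit 11 assessments. The output templates (SAP 8) are not available and might carry a definition.
- **Outcomes are not equally exposed.** An event that caused withdrawal normally began before the Discontinuation Visit. It enters the follow-up tables only if observed events include ongoing ones, which SAP 17.1 does not define. Nothing in the documents shows worse global status among stoppers.
- **It is not the only comparison involving time off drug.** Baseline 1 comes from before dosing in the earlier study, so change from it is a within-subject comparison. CBD status is at most the only concurrent between-subject one.
- **Recovery is not hidden.** Laboratory data are listed with abnormal values flagged, listings include unscheduled and early-discontinuation data (SAP 6.3 and 17.3), and disposition gives the reasons for leaving (SAP 9). What is missing is a group summary.
- **The tables are descriptive.** SAP 6.5 and 17 rule out inference and statistical safety comparisons, so no planned estimate is biased.

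All of this stands and limits the claim. It does not supply the missing allocation rule, nor remove the overlap in the liver table. The SAP itself sets continuing against stopping, and no caveat about self-selection is planned in the SAP text.

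**Conclusion.** The point holds in limited form. CBD status in SAP 7.4 is incompletely defined, and it does not separate early discontinuers from completers who stopped. If early discontinuers are counted as stopped, the columns are not comparable, most clearly for markedly abnormal liver tests. For other outcomes the extent cannot be determined.

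The size is unknown. The documents give no withdrawal rate, no number entering Expanded Access and no persistence of liver abnormality at two weeks. The range of −0.9 to +32.4 points comes from assumed inputs, and even its sign is not fixed. It shows only that a few subjects could dominate a small column. The consequence is a risk of misreading supplementary tables; the main safety summaries over the treatment period do not depend on this split. The change is worth making before database lock because it is cheap.

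**What to change.** In SAP 7.4, define CBD status from the last dose date and the date of Expanded Access entry, in three groups:

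1. completed treatment and continued CBD;
2. completed treatment and stopped, including a planned taper that ended before Visit 10;
3. discontinued treatment early, including subjects who stopped treatment but kept attending visits.

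Limit any reading of continuing against stopping to groups 1 and 2, and footnote every such table to say that the groups are self-selected. In SAP 17.1, define follow-up TEAEs by onset after the Final visit.

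For laboratory values at Visit 11, add change from the last on-treatment value beside the two existing baselines. State the rule for tapered subjects: Visit 10 falls after their last dose, so their last scheduled on-treatment sample may be the Week 36 one.

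The data are already collected: end of treatment and its reason (SAP 9 and 14) and the Expanded Access date (SAP 3.1). The PK plan already flags Expanded Access subjects. The cost is SAP wording and one more column in the shells. The downside is smaller columns in a study of at most 80 subjects (60 + 20).

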8. OUTPUT PRESENTATIONS

The templates provided with this SAP describe the presentations for this study and therefore the format and content of the summary tables, figures and listings to be provided by [REDACTED] Biostatistics.

9. DISPOSITION AND WITHDRAWALS

All subjects who provide informed consent will be accounted for in this study.

Subject disposition and withdrawals, and protocol violations, including inclusion and exclusion criteria will be presented for the ENR set.

The table will summarize the following information:

- Number of subjects screened
- Number of screen failures - overall and by following reasons:
 - subject did not meet eligibility criteria
 - Withdraw informed consent
 - Subject died
 - Other
- Number of treated subjects (SAF)
- Number of subjects in the PK
- Number of subjects who completed study including follow-up
- Number of subjects who discontinued from treatment (overall and by reasons)
- Number of subjects with early discontinuation from study (overall and by reasons)

For both discontinuation from treatment/study the reasons are as follows:

- Inadvertently enrolled (enrollment criteria not met)

Document: C:\Users\q832483\Documents\Insy CSR\Pending\Ready for QC\New folder\Statistical Analysis Plan.docx
Author: [REDACTED] Version Number: V1.0 Final
Version Date: 04APR2017

Template No: CS_TP_BS016 – Revision 3
Effective Date: 01May2012

Reference: CS_WI_BS005

- Investigator decision
- Adverse Event
- Subject withdrew consent
- Lack of protocol compliance
- Subject attempted suicide or is at risk of suicide
- Sponsor decision
- Subject becomes pregnant
- Abnormal laboratory values
- Lost to follow-up
- Death
- Other

The following important (clinically) protocol deviations, as identified in the clinical trial management system (CTMS), will be summarized:

- Administrative Criteria
- Eligibility and Entry Criteria
- IP Compliance
- Informed Consent
- Laboratory Assessment Criteria
- Serious AE Criteria
- Study Procedures Criteria
- Regulatory or Ethics Approvals Criteria
- Visit Scheduled Criteria
- Other Criteria

Supportive listings will also be provided:

- Allocation to treatment
- Protocol deviations
- Subjects eligibility criteria

10. DEMOGRAPHIC AND OTHER BASELINE CHARACTERISTICS

Demographic data and other baseline characteristics will be presented for the SAF by age category and overall.

No statistical testing will be carried out for demographic or other baseline characteristics.

The following demographic and other baseline characteristics will be reported for this study:

Document: C:\Users\q832483\Documents\Insy CSR\Pending\Ready for QC\New folder\Statistical Analysis Plan.docx
Author: [REDACTED] Version Number: V1.0 Final
Version Date: 04APR2017

Template No: CS_TP_BS016 – Revision 3
Effective Date: 01May2012

Reference: CS_WI_BS005

- Age (years) - calculated relative to date of consent
- Gender
- Race
- Ethnicity
- Weight (kg)
- Height (cm)

For height and weight, the baseline value of the previous study will be reported for subjects who were enrolled no later than 14 days after they completed their previous study. Otherwise, height and weight will be from the screening physical examinations for this study.

10.1. DERIVATIONS

- Age (years) = integer portion [(calculated relative to date of signed informed consent – date of birth)/365.25]

11. SURGICAL AND MEDICAL HISTORY

Past and current surgical and medical history, as recorded on the *Medical and Surgical History* eCRF page, will be summarized by age category and overall using the System Organ Class (SOC) and Preferred Term (PT) as coded using the latest version of the Medical Dictionary for Regulatory Activities (MedDRA).

Past medical and surgical conditions are those which stop prior to the first dose of study medication. If both a past and current (ongoing) medical condition records are indicated for a condition, the condition will be presented under current medical conditions only.

A supportive listing will also be provided.

12. PRIOR AND CONCOMITANT PROCEDURES

Prior and concomitant procedures, as collected on the *Concomitant Procedure* eCRF page, will be summarized for the SAF, by age category and overall. They will be presented by PT and coded using the latest version of MedDRA.

- 'Prior' procedures are procedures which started and stopped prior to the first dose of study medication.
- 'Concomitant' procedures are procedures which:
 - Started prior to, on or after the first dose of study medication and started no later than 6 days following end of study medication (Unless the procedure is related to SAE. In such a case the procedure can start within 30 days after last study visit.),
 - AND ended on or after the date of first dose of study medication or were ongoing at the end of the study.
- 'Post' procedures are procedures which started later than 6 days following end of study medication.

Document: C:\Users\q832483\Documents\Insy CSR\Pending\Ready for QC\New folder\Statistical Analysis Plan.docx
Author: [REDACTED] Version Number: V1.0 Final
Version Date: 04APR2017

Template No: CS_TP_BS016 – Revision 3
Effective Date: 01May2012

Reference: CS_WI_BS005

Prior and concomitant procedures observed during the Follow-up period will also be summarized by CBD status.

Prior and concomitant procedures will also be listed.

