3.3 Schedule of Events

The Schedule of Events may be found in Table 1.

Subjects should rollover from the previous study as soon as possible following completion of Day 11 activities (INS011-14-029) or when appropriate for INS011-15-054 to avoid interruption of the investigational product. A Screening Visit may be required for all subjects that do not rollover within 14 days of completing their previous study. The duration of each subject's treatment will be determined by the duration of treatment the subject received in their previous study as described in Section 3.1.

Visits will occur weekly for two weeks, monthly for 3 months, and then quarterly thereafter. A Screening Period (Visit 1) may be required for all subjects that do not rollover within 14 days of completing their previous study. All subjects will complete a Final Visit/Discontinuation Visit regardless of when they stop treatment/complete the study. Discontinuation may occur due to reasons discussed in Sections 3.1 and 3.4.3. A Follow-up Visit will occur 2 weeks after the Final Visit/Discontinuation Visit.

Table 1 Schedule of Events

Assessments ^a	Visit 1 (14 Day Screening Period ^b)	Treatment Period						Final Visit / Discontinuation Visit ^d (Visit 10) Week 48 ±10 days ^e (if not conducted at a normally scheduled visit)	Follow-up Visit Two weeks after Final Visit / Discontinuation Visit (Visit 11) ±5 days
		Visit 2 (Day 1 ^c)	Visit 3 (Week 1) ±3 days	Visit 4 (Week 2) ±3 days	Visits 5, 6, & 7 Monthly: (Weeks 4, 8 & 12) ±7 days	Visits 8, 9, Quarterly: (Weeks 24 and 36) ±10 days ^d			
Obtain informed consent ^f	X	X							
Demographics	X	X							
Review of inclusion/exclusion criteria	X	X							
Medical and surgical history	X	X							
Assessment of current AEDs	X	X	X	X	X	X		X	X
Concomitant medications and procedures	X	X	X	X	X	X		X	
ECG	X	X						X	
Vital signs ^g	X	X	X	X	X	X		X	X
Laboratory values (hematology, chemistry) ^h	X	X				X		X	X
Urinalysis ⁱ	X	X				X		X	X
Pregnancy test ^j	X	X				X		X	X

Assessments ^a	Visit 1 (14 Day Screening Period ^b)	Treatment Period						Final Visit / Discontinuation Visit ^d (Visit 10) Week 48 ±10 days ^e (if not conducted at a normally scheduled visit)	Follow-up Visit Two weeks after Final Visit / Discontinuation Visit (Visit 11) ±5 days
		Visit 2 (Day 1 ^c)	Visit 3 (Week 1) ±3 days	Visit 4 (Week 2) ±3 days	Visits 5, 6, & 7 Monthly: (Weeks 4, 8 & 12) ±7 days	Visits 8, 9, Quarterly: (Weeks 24 and 36) ±10 days ^d			

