5.4 Follow-up Visit (Visit 11) ±5 days

All subjects will complete a Follow-up Visit 2 weeks (± 5 days) after the Final Visit/Discontinuation Visit. The following activities will be completed:

- Record recent medication history including current AEDs, vitamins, herbal preparations, blood products, and over-the-counter drugs
- Record vital signs (blood pressure, heart rate, respiratory rate, and temperature measurements)
- Draw blood samples for hematology and chemistry (fasting NOT required) and record whether subject was fasting at time of collection in the eCRF
- Obtain a urine sample for urinalysis
- Obtain a urine sample for serum β -hCG pregnancy test in female subjects of childbearing potential
- Perform physical examination (see Section 6.1.5.2), including height and weight
- Perform a brief neurology examination (see Section 6.1.5.2)
- Record AEs and SAEs

- Complete blood draw for plasma levels
- Administer Investigator CGI-I and CGI-S
- Administer parent(s)/caregiver(s) CGI-I and CGI-S
 - When appropriate, subjects will complete the CGI-I and CGI-S for themselves.
- Administer IPES
 - The IPES is validated for subjects who are 2 to 16 years of (developmental) age. Due to developmental delay characteristic of the study population, subjects through 18 years of chronological age will complete the IPES.
- Administer C-SSRS (if appropriate).

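### SAP 12 tabulates follow-up-period procedures by CBD status, but procedures are not systematically collected after Visit 10 and the 6-day rule removes many that might be recorded

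*SAP*

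**What the plan says.** SAP Section 12 takes its data from one form: "Prior and concomitant procedures, as collected on the *Concomitant Procedure* eCRF page". After the main summary by age category it adds: "Prior and concomitant procedures observed during the Follow-up period will also be summarized by CBD status". SAP 7.4 sets the follow-up period as the interval from the Final visit to the Follow-up visit. It sets CBD status as continuing versus stopping cannabidiol after the Final visit.

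SAP 12 sorts procedures into three classes. Prior procedures start and stop before the first dose. Concomitant procedures must, among other conditions, have "started no later than 6 days following end of study medication", with an exception for SAE-related procedures up to 30 days after the last study visit. Post procedures start later than those 6 days. The by-CBD-status sentence names only the first two classes.

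In the protocol, Table 1 has a row "Concomitant medications and procedures", marked from Visit 1 through Visit 10 and empty at Visit 11. Section 5.3 (Visit 10) instructs sites: "Record concomitant medications and concomitant procedures". Section 5.4 (Visit 11) has no such item. Its nearest entry is "Record recent medication history including current AEDs, vitamins, herbal preparations, blood products, and over-the-counter drugs". On timing, Section 5.4 says: "All subjects will complete a Follow-up Visit 2 weeks (± 5 days) after the Final Visit/Discontinuation Visit".

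**The concern.** Visit 11 is the only scheduled contact that looks back over the interval the SAP table describes, and at that contact sites are not told to record procedures. A sparse table could mean that few procedures took place or that they were not recorded, and nothing in SAP 12 warns the reader of this.

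The CBD-status split sets subjects who stop beside those who continue. If capture is incomplete, and more so in one group, the display can mislead even though it is only descriptive. What lacks an instructed route into the database is the non-serious procedure not tied to an adverse event. One example is a change of VNS settings, which Protocol 4.3 permits, if a site would log it as a procedure.

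**Working it through.** The plan states no figure on this point, so the check is a comparison of the texts plus one proportion.

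**Step 1. Is procedure recording scheduled after Visit 10?**

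| Place | Visits 1 to 10 | Visit 11 |
|---|---|---|
| Table 1, row for concomitant medications and procedures | marked | blank |
| Table 1, row above it (current AEDs) | marked | marked |
| Visit lists in Sections 5.1, 5.2.1 to 5.2.5, 5.3 | procedures item in all seven | – |
| Visit list in Section 5.4 | – | no procedures item |

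The AED row is marked at Visit 11 and Section 5.4 agrees with the blank cell, so the blank is not an artefact of reading the table. Scheduled collection points for procedures inside the follow-up period: 0.

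**Step 2. Which procedures could SAP 12 place in the table?**

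A Prior procedure ended before the first dose, so it cannot fall in the follow-up period. That leaves Concomitant procedures: those already ongoing at Visit 10, those starting within the 6-day window, and SAE-related ones under the 30-day exception. A non-SAE procedure starting later is Post and is left out, even if recorded.

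**Step 3. How much of the follow-up period does the 6-day window cover?**

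Inputs: window 6 days (SAP 12); length of follow-up L = 14 days, range 14 − 5 = 9 to 14 + 5 = 19 (Section 5.4). Let k be the number of days from last dose to Visit 10. The documents do not fix k, so it is an assumption.

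Share covered = max(0, 6 − k) / L

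| k (assumed) | L = 9 | L = 14 | L = 19 |
|---|---|---|---|
| 0 (last dose on day of Visit 10) | 6/9 = 67% | 6/14 = 43% | 6/19 = 32% |
| 3 | 3/9 = 33% | 3/14 = 21% | 3/19 = 16% |
| 6 or more | 0% | 0% | 0% |

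Protocol 4.1.2 says subjects not continuing under Expanded Access may be tapered, with the taper completed before Visit 10. Tapered subjects therefore have k above 0, and they are in the stopping group. If continuing subjects take their last study dose at about Visit 10 (assumption), their window is longer.

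**Step 4. Would collection at Visit 11 be enough?**

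No. With k = 0 and L = 14, a non-SAE procedure starting on any of the last 14 − 6 = 8 days would be recorded, classed as Post, and still be absent from the table.

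**The case against.** A reader might infer that nobody asks about anything after Visit 10, that both CBD-status groups will show close to zero procedures, and that this will pass as evidence of no excess after withdrawal. The documents do not support that reading.

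- AEs and SAEs are recorded at Visit 11 (Table 1, Section 5.4) and elicited by questioning at each visit (Section 6.1.2). SAEs spontaneously reported within 30 days of the last visit are also collected. SAP 12 admits SAE-related procedures up to 30 days after the last visit, so some later entries were clearly expected.
- The eCRF is not among the documents. If the procedure page is a running log, sites could add later procedures, although no protocol text prompts them to at Visit 11.
- No procedure rate is given, so the number missed is unknown and a near-zero count is only a prediction.
- Post-withdrawal safety does not rest on this table. Inpatient admissions are SAEs unless planned for existing disease, and seizures that differ significantly from baseline are AEs (Section 6.1.1). The SAP presents follow-up TEAEs by CBD status (17.1, except those leading to interruption or discontinuation). It does the same for AEDs (13), deaths (17.2), laboratory results (17.3), vital signs and weight (17.5), and CGI and IPES (16.2.2.3).
- SAP 6.5 rules out inference, so the table is a side-by-side display and not a formal comparison.

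All of this stands, and it limits the consequence. It does not remove the mismatch: the partial route through adverse events makes the entries selectively event-driven, and the table carries no label saying so.

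**Conclusion.** The point holds as a minor inconsistency between protocol and SAP. Scheduled procedure collection ends at Visit 10, while SAP 12 reports on the 9 to 19 days that follow, in up to 80 subjects (the protocol's stated maximum). A low count there cannot be told apart from non-collection.

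The 6-day rule adds a second, separate loss. Non-SAE procedures are eligible for 43% of a 14-day follow-up if the last dose is at Visit 10 (32% to 67% over the visit window), and for none of it if a taper ended 6 or more days earlier. Both figures depend on the assumed date of last dose. The undercount may therefore differ by CBD status; the documents do not show that it will, or by how much.

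One descriptive table is affected. None of the safety endpoints listed in Protocol 6.1.6 depends on it. Confidence is high in the mismatch and low in any particular misreading of the table.

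**What to change.** If Visit 11 is still to come for subjects, make two changes together:

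1. Protocol: add the Section 5.3 item "Record concomitant medications and concomitant procedures" to Section 5.4, and mark Visit 11 in the matching row of Table 1.
2. SAP 12: have the follow-up table by CBD status include Post procedures that start between the Final and Follow-up visits. Eligibility is then set by the two visits and not by the date of last dose, so the whole interval is covered in both groups.

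The cost is one question at an existing visit, an eCRF page that already exists, and one SAP sentence. No clinical procedure is added.

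If Visit 11 has already passed, delete the follow-up table by CBD status from SAP 12. Alternatively, restrict it to procedures linked to a recorded AE or SAE, including those classed as Post, because the 6-day rule would otherwise drop procedures for non-serious AEs. Footnote that procedures were not systematically collected after Visit 10. The cost is one table removed, or one restriction and a footnote.
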